# **Other Investigators and Study Personnel:**

[name]. †, M.D., [name]., M.P.H., [name], M.A.\* [name], A.P.R.N. †, [name], R.N.\*, [name] RN, BSN, MBA\*, [name], M.S., RN\*, [name].,\* [name], Psy.D., [name], B.S.\* [name]. †, [name]. †, [name], B.A.\*, [name], B.A.\*, [name], B.A.\*, [name], M.A.\*, [name], B.A.\*, [name].\*, [name].\*, [name].\*, [name], M.A.\*, [name]\*, [name], M.S.\*, [name], M.S.\*, [name], MMS\*

- \* Individuals who will be obtaining consent
- † Individuals authorized to prescribe study medication
- \* Individuals who will be obtaining consent
- † Individuals authorized to prescribe study medication
- **2. Title of Project:** An Investigation of the Effects of Riluzole in Patients with Post-Traumatic Stress Disorder (PTSD).
- **3. Purpose:** To conduct a pilot study evaluating the efficacy of riluzole 50 mg twice per day in decreasing symptoms of PTSD in patients diagnosed with PTSD.

Post Traumatic Stress Disorder (PTSD) is a debilitating and chronic mental illness with limited treatment options. Currently, there are only two FDA-approved medications both of which are monoaminergic antidepressants. Rates of non-response to these medications are high. The current study aims to examine the efficacy of a novel drug, riluzole, in treating PTSD symptoms. Riluzole is an FDA approved medication for Amyotrophic Lateral Sclerosis. Preclinical studies have shown riluzole to modulate glutamate release and clearance, and to have potent neuroprotective properties, promoting neuro-resilience. Other preclinical data also show the drug to have anxiolytic-like and antidepressant-like effects in rodent models of stress used to screen for antidepressant and anxiolytic activity. In addition, several open-label clinical studies further suggest riluzole has anxiolytic and antidepressant properties, even in patients who do not respond to standard monoaminergic antidepressant and anxiolytic medications. However, to date, riluzole has not been studied in patients suffering from PTSD. The proposed study will provide pilot data on the efficacy of riluzole in PTSD.

**4. Hypothesis:** We predict that riluzole will significantly reduce the symptoms of PTSD (measured by the Clinician Administered PTSD Scale-CAPS scores).

SPECIFIC AIM 1: To provide preliminary data about the efficacy of riluzole treatment in improving PTSD symptoms. *Hypothesis*: PTSD subjects treated with

riluzole (50 mg twice per day for 12 weeks) will have reduction in PTSD symptoms. To examine the efficacy of riluzole we will compare the mean change in the CAPS total score over the course of 12 weeks of riluzole treatment.

# 5. Background:

PTSD Is a Debilitating Illness with Limited Treatment Options

The House Veterans Affairs Committee issued a report in mid October 2006 stating that the number of Iraq and Afghanistan veterans seeking help for PTSD has gone from 4500 to 9000 from October 2005 through June 2006. In the general adult population, PTSD has a lifetime prevalence rate ranging from approximately 5 - 10%. PTSD tends to be a chronic disorder with one third of sufferers having symptoms more than ten years after experiencing the traumatic event. The symptom profile for PTSD includes avoidance, arousal and re-experiencing symptoms.

Despite the disabling and chronic nature of PTSD, only two medications, both of them selective serotonin reuptake inhibitors (SSRIs), have FDA-approval for PTSD treatment. However, accumulating evidence highlights the limitation of SSRI treatment and the prevalence of SSRI-resistant PTSD.

Riluzole Is A Glutamate Modulating Agent With Anxiolytic And Antidepressant Effects.

Over the last two decades, convergent lines of research have demonstrated aberrant glutamatergic function in mood and anxiety disorders. These neurobiological findings have been underscored by preliminary trials showing promising results for novel drugs with glutamate-based mechanisms. One such medication is riluzole, an agent possessing neuroprotective properties  approved by the United States Food and Drug Administration for treatment of Amyotrophic Lateral Sclerosis. Riluzole is believed to exert its pharmacological effects primarily by reducing pre-synaptic glutamate release and potentiating glutamate reuptake . In open-label trials at Yale and other institutions, riluzole showed significant anxiolytic properties in patients with major depression , bipolar depression , obsessive-compulsive disorder , and generalized anxiety disorder (GAD)  (for review see references. ). However, to date, riluzole was not studied in patients with PTSD.

**6. Significance of proposed research:** Our proposed study is the first to examine the effect and feasibility of riluzole treatment for PTSD. Data from this pilot study will inform the design of future larger double-blind controlled studies. For e.g., if PTSD veterans showed full early response to riluzole following 1-4 weeks, this will affect the design of future definitive (likely multisite) studies. While placebo-controlled studies are standard for FDA approval and definitive clinical trials confirming efficacy, an open label approach is appropriate for pilot studies seeking early signals of efficacy and optimal treatment regimen. Pilot open label studies are essential for early phase of drug development.

**7. Experimental subjects**: We anticipate approximately 20 male and female subjects with PTSD, between the ages of 18-75 years, to complete all study procedures. In order to account for screenings failure and subject drop outs, and retain a sample of 20 subjects completing the treatment phase, approximately 50 eligible subjects will be enrolled.

# Inclusion Criteria:

- Male or female subjects between the ages of 18-75 years;
- Able to provide written informed consent;
- Current Post Traumatic Stress Disorder, as determined by the Clinician Administered Scale for PTSD, or the presence of sub-threshold PTSD. Individuals with sub-threshold PTSD will be included at the discretion of the PI;
- Clinician Administered PTSD Scale (CAPS) score of 23 or higher;
- Be able to understand and speak English.
- Subjects taking FDA-approved antidepressant medications may enter the study if they have been on a stable dose for at least 4 weeks prior to starting the study drug.

### Exclusion Criteria:

- Breastfeeding women and pregnant women, or women of child bearing potential who are not using a medically accepted means of contraception (to include oral, injectable, or implant birth control, condom, diaphragm with spermicide, intrauterine device, tubal ligation, abstinence, or partner with vasectomy);
- Current, ongoing serious suicidal risk as assessed by evaluating investigator or by scoring 5 or more on the item-10 of the MADRS.
- Unstable medical illness as determined by the investigator;
- Patients with schizophrenia or schizoaffective disorders (current or past);
- Substance use disorder during the 3 months prior to screening; except for Cannabis and Alcohol use Disorders.
- Clinical evidence of untreated hypothyroidism;
- Patients with any evidence of clinically significant liver abnormalities, or any liver transaminase level > 1.5 x ULN at initial screening, or > 5 x ULN during treatment;
- Axis II personality disorders that are the primary purpose of treatment, or would interfere with a patient's safety or compliance, as determined by the investigator during open-ended psychiatric interview;
- Patients currently being treated for a respiratory disorder (including asthma or COPD);
- For participants over the age of 60, evidence of dementia as determined by the St. Luis University Mental Status Exam (SLUMS; participants with total scores less than or equal to 20 will be excluded and referred to their Primary Care Physician for follow-up/dementia evaluation);

Structured psychotherapy focused on treatment of PTSD is exclusionary unless the subject has had at least 8 weeks of treatment prior to starting the study medication;

[figure not shown]
- **8. Privacy:** All reports generated from the data obtained through this study will protect the confidentiality of the subjects who participate in this study. All subjects will be given a "wallet card" which identifies them as a study participant and lists the emergency contact numbers. If a subject shows clinical deterioration (worsening of PTSD symptoms), [name] will determine whether: 1) the subject can remain in the study, or; 2) a higher level of care (e.g. referral back to treating psychiatrist or referral to emergency or inpatient care) is needed.
- **9. Selection**: Subject eligibility will first be assessed via telephone screening and if records are available, by a preliminary medical record review. If the subject seems to be a likely candidate for inclusion in this protocol, he or she will be evaluated for study eligibility in person. Telephone screens will occur by experienced research personnel adept with this process. Following a face-to-face evaluation and discussion with the research team, an experienced study investigator will determine suitability for enrollment.
- 10. Recruitment: Subjects will be recruited through flyers, public advertisement (newspaper, radio, internet posting), by word of mouth, contact with community service groups, our local IRB-approved screening protocol (KW0003), and clinics and local treatment facilities (e.g., VA Hospital, Community-Based Outpatient Clinics, local private practices). Subjects will be identified via their response to advertisements and/or internal recruiting through the research clinics. Subjects will be asked to call us at the number provided on the flyers if they are interested in participating in the research study. Subjects will be contacted for follow-up appointments via the most convenient means and personal preference, e.g. telephone. All available research staff is responsible for recruiting potential subjects.
- 11. Research Plan: This study will be conducted at the VA Hospital, West Haven, CT.

Overview: This is a diagnosis-informed study designed to provide preliminary data regarding the efficacy and tolerability of riluzole to treat symptoms of PTSD. Subjects diagnosed with PTSD will receive riluzole, 50 mg taken twice daily (BID) for 12 weeks. PTSD subjects will be followed closely on a weekly basis and their liver function and pregnancy tests will be repeated (see Table 1).

Dosing: Following confirmation of eligibility, the dosing regimen for the first week of study medication is 50 mg twice a day (BID). Subjects who are unable to tolerate the study medication will be allowed to take a lower dose. For these subjects, the dose may be lowered to 50 mg taken once a day (QD). Subjects who are unable to tolerate the once a day 50 mg (QD) dosing regimen will be discontinued from the study. Riluzole should be taken 1 hour before or 2 hours after a meal to avoid food-related decreases in bioavailability.

A schedule of the study events is provided in Table 1.

Figure 1. Study Design

- A. Participants: Twenty patients with a current diagnosis of PTSD or sub-threshold PTSD between the ages of 18-75 will complete the treatment phase of the study. Subjects will initially be pre-screened by phone interview and a preliminary medical record review. Eligible subjects will then be invited for an in-office visit and will complete the written informed consent process. Subjects will be thoroughly screened for inclusion and exclusion criteria as described below.
- B. Discontinuation of subjects: Subjects may be discontinued from study treatment and assessments at any time. Specific reasons for discontinuing a subject from this study are:
  - Voluntary discontinuation by the subject, who is at any time free to discontinue his/her participation in the study without prejudice to further treatment;
  - Clinical deterioration: The following are objective criteria for clinical deterioration, (1) a 35% increase in CAPS scores at any time during the study, (2) Patients with a CGI-I score ≥ 6 at any post-baseline visit, and (3) the onset of active suicidality as assessed by the study investigator or by scoring 5 or more on the item-10 of MADRS;
  - Evidence of neutropenia (ANC ≤ 1500) or other intolerable adverse reaction, or unable to tolerate study drug;
  - Transaminase levels > 5x ULN;
  - Safety reasons as judged by the investigator;
  - Stopping birth control or positive pregnancy test;
  - Evidence of illicit drug abuse (except for cannabis) or problematic alcohol use during trial;
  - Non-compliance to protocol as judged by the investigator; Subjects who do not take between 75-125% of study medication for two consecutive visits are considered non-adherent and are withdrawn from the study medication.

A subject that prematurely discontinues (i.e. stops study medication or no longer wishes to participate) will always be asked about the reason(s) for discontinuation and the presence of any adverse events. If possible, they will be seen and assessed by the investigator. Adverse events will be followed up as medically necessary.

- C. Screening Procedures and Behavioral Assessments: A waiver of HIPAA authorization and written informed consent will be obtained for a brief initial phone screen and preliminary medical record review. The phone screen and preliminary medical record review will be done to determine obvious exclusions from the study protocol and to prevent subjects from making unnecessary travel for screening as well as possibily delaying the start of other treatments. Potentially eligible subjects will then be invited for an in-office screening visit, sign the VA informed consent, the VA HIPAA, be personally interviewed and begin the medical assessments. All subjects will have an initial screening assessment that includes medical history, physical examination, laboratory testing, psychiatric history and standardized psychiatric assessments.
- C.1. Historical and Demographic Information: Each subject will complete a demographic information form. This document will elicit information about the subjects' demographics including education level, socioeconomic status, race and ethnicity. In addition, it will also request information on the subject's family history of mental illness.
- C.2. Screening Physical Exam and Laboratories: All subjects will have a standard physical examination (including neurological examination) conducted by a physician/APRN at the time of the initial screening. Routine laboratory studies include CBC, CMP, baseline HCG, TSH, fT4, RPR, ESR, CRP, urinalysis, and urine toxicology screen. An ECG will also be obtained. Additional tests will be requested as clinically indicated.
- C.3. Screening and Behavioral Assessments: PTSD subjects will have an open ended psychiatric interview, in addition to a structured clinical interview (i.e. SCID or MINI). Baseline and follow-up ratings will also be obtained via assessment measures of PTSD, trauma, depression, anxiety, sleep, alcohol use, and adverse effects. Subjects will also complete a computerized neuropsychological test battery called 'Cogstate' (see Table 1).

It is estimated that the total amount of time required by the patient to determine screening eligibility will be 7 hours. It will require one hour of time to complete each of the scheduled CAPS interviews. Repeated follow-up visits (including rating scales, blood work, urine screens, etc.) without the above cited assessments, will last for approximately 45 minutes to one hour. If necessary due to time commitments or difficulties with scheduling, some visits may take place over more than one day during the study week.

Each of the psychiatric, behavioral and cognitive assessment instruments is briefly described below.

- 1. Clinician Administered PTSD Scale (CAPS): The CAPS is a standardized clinician-rated instrument to assess the presence and severity of PTSD symptoms.
- 2. Post Traumatic Stress Disorder Checklist (PCL): The PCL is used to measure PTSD symptoms and is a self-report questionnaire that shares similar reliability with the CAPS.
- 3. The Combat Exposure Scale (CES): The CES is a self-report instrument that measures reports of wartime stressors on a 5 point Likert Scale format.
- 4. Early Trauma Inventory (ETI-SR) The ETI-SR is a self-report instrument to assess childhood trauma and includes physical, emotional and sexual abuse as well as general traumas.
- 5. Klein Loss Scale (KLS): The KLS is a self-report of parental loss or separation during childhood.
- 6. Global Perceived Early Life Stress (GPELS): The GPELS is a self-report of perceived stress during childhood.
- 7. Montgomery-Asberg Depression Rating Scale (MADRS): The MADRS is a standardized instrument to ascertain depressed mood and neurovegetative signs and symptoms of depression.
- 8. *Quick Inventory of Depressive Symptoms Self-Report* (QIDS-SR): The QIDS-SR is a patient-rated depression instrument.
- 9. Massachusetts General Hospital Antidepressant Treatment History Questionnaire (MGH-ATRQ)-This is a self-rated questionnaire used to determine treatment resistance in major depressive disorder.
- 10. Clinical Global Impressions Scale (CGI) and the Patient Global Impressions Scale (PGI): The CGI and PGI are widely used instruments, which assess overall severity of illness on a 1 to 7 point scale with 1 indicating "normal, not at all ill" and 7 indicating "among the most extremely ill patients." These instruments also assess global improvement on a 1-to-7 point scale with 1 indicating "very much improved," 4 indicating "no change" and 7 indicating "very much worse."
- 11. Penn State Worry Questionnaire (PSWQ): The PSWQ is a self-report questionnaire to assess for 'worry' symptoms that are typical of generalized anxiety.
- 12. Pittsburgh Sleep Quality Index (PSQI): The PSQI is a self-report questionnaire to assess sleep quality and sleep disturbance.
- 13. Sheehan Disability Scale (SDS): The SDS is a brief self-rated measure of disability and impairment.
- 14. Columbia-Suicide Severity Rating Scale (C-SSRS): The C-SSRS is a brief clinician administered and standardized measure that uniquely assesses essential information about suicide behavior, ideation, lethality and severity, and distinguishes between suicidal occurrences and non-suicidal self-injury.
- 15. Cogstate is a brief computerized neuropsychological test battery. We will administer the following subtests from this battery to assess working memory,

- visual motor function, visual attention executive function, verbal learning/memory and visual learning/memory: One Back and Two Back Test, Chase Test, Identification Task, Groton Maze Learning Test (with delayed recall), the International Shopping List Task (with delayed recall) and the One Card Learning Task.
- 16. St. Luis University Mental Status Exam (SLUMS) The SLUMS is a dementia screening instrument. It will be administered to participants who are 60 or older during our screening process.
- 17. Modified Military Acute Concussion Evaluation (MACE) The MACE is a concussion screening tool for the acute assessment of service members involved in a potentially concussive event.
- 18. Alcohol and Consumption Habits—This is a brief measure that documents alcohol, caffeine and nicotine habits.
- 19. Systematic Assessment for Treatment Emergent Events (SAFTEE): The SAFTEE is a commonly used instrument originally developed by NIMH and adapted into a self-report instrument. It examines, in systematic fashion, possible treatment-emergent side effects and probes for specific adverse symptoms, including suicidal thoughts and behaviors, and self-injurious behavior.
- 20. Drug Attitude Inventory- (DAI): The DAI evaluates how attitudes about medications may affect treatment adherence. The items with the most potential for discrimination between dosing compliance and noncompliance are related to subjective 'feeling' factors.
- 21. Perceived Stress Scale (PSS): This is a 10-item self-report questionnaire to assess the severity of perceived stress over the past month.
- 22. Cumulative Adversity Interview (CAI): A multifaceted semi-structured assessment of stressful life events and chronic subjective stress used in research on stress and psychopathology.

Due to the potential of Riluzole to cause elevations in serum aminotransferase levels, liver function tests will be reviewed and monitored for medical significance (marking NCS for results not clinically significant) by the PI, a co-investigator or other medical research personnel (A.P.R.N., R.N. etc.). If any liver transaminase level is > 5X the UNL, the study investigator will be informed and the patient will be discontinued from the study, with appropriate medical follow-up.

PTSD subjects receiving the study medication will be seen weekly. Compliance with study medication will also be assessed weekly and at each visit. Subjects will be given medication diary cards to record the medication that they have taken at each daily dosing interval and the medication that was missed at each dosing interval. Drug accountability will then be done between the medication that was returned and the medication recorded as being taken on the diary cards. A subset of the interviews and measures obtained throughout the study will be repeated at a one-month, in person follow-up. This follow-up will be used to evaluate any lasting effects of the treatment, if any.

The presence of any spontaneously reported side effect or adverse event is carefully documented. Reasons for premature discontinuation of study medication, including intolerable side effects, are recorded; however, all willing subjects continue to return for weekly evaluations as if they remain on study medication.

All concomitant medications taken during the study are also recorded in the paper research chart, along with dosage information and start and stop dates. Medication management and clinical ratings are performed by the study physician/APRN and the clinical rater, respectively.

Subjects who are unable to tolerate the study medication after adjusting the dosing regimen to the lowest dose of 50 mg QD are withdrawn from study medication. Treatment adherence is monitored by pill counts. In order to minimize risks, subjects are advised during the consenting process that if they discontinue the study medication prematurely, the researchers want them to continue study evaluations as if they were still on the study medication for reasons of safety monitoring (i.e. to evaluate the possibility of withdrawal effects from abrupt discontinuation of the study drug, worsening of psychological symptoms or other newly emergent medical symptoms after stopping the study drug). Non-adherent patients are classified as dropouts in the analysis.

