Protection Against Risks: All clinical raters have experience in clinical psychiatric assessment and will make every effort to implement protocol procedures in a sensitive and supportive manner. Research interviews will be interrupted if subjects become distressed or object to answering questions. Other measures to minimize risks include the careful assessment of each subject before the study, and close clinical scrutiny during all aspects of the study. Screening for suicide risk factors and suicidality is described in the research design.

Weekly contact is maintained throughout the clinical trial. A study staff member will call participants, during any week in which there is no clinic visits, to help ensure subject safety and protocol adherence.

We have included safety measures such as discontinuation of the study drug and transition to standard clinical treatment should subjects worsen to a sufficient degree. These precautions are likely to be highly effective in minimizing risks. Subjects may be hospitalized if they have a worsening of their symptoms, including becoming suicidal. In this case or if subjects discontinue study medication they will receive standard short-term clinical treatment as indicated.

Due to the potential of riluzole to cause elevations in serum aminotransferase levels, subjects will have liver function tests performed prior to initiating the trial and monthly for the duration of the study, or more frequently if clinically indicated. Patients with any evidence of clinically significant liver abnormalities or any liver transaminase level > 1.5 x ULN at baseline will be excluded from the study. Subjects will be discontinued from the study if any LFT measure rises above 5 x the ULN once treatment has been initiated. This is the recommendation in the PDR and is what has been used in previous studies. If treatment is terminated due to physical risks, subjects will be followed carefully until resolution of symptoms and treated with the follow up care described in the protocol.

Subjects will also be asked to report any cough, difficulty breathing or chills to the study staff in order to monitor for the possible emergence of interstitial lung disease or hypersensitivity pneumonitis. The study investigator, physician/APRN, and rater ask patients about any new symptoms at every visit.

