Suicidal Ideation and Imminent Harm: Despite treatment, people with PTSD may get worse. All communications about suicide and threats are taken seriously. It is important to assess the risk of suicide carefully when working with these individuals. Many subjects may admit to fleeting thoughts of death or briefly wishing for death; these thoughts need to be considered in context of the subject's overall history, along with a consideration of other risk factors for suicide. Study clinicians will assess patients at each visit for suicide risk and potential. Individuals at such risk will be treated appropriately, including options such as increased contact, more frequent clinical visits, or emergent psychiatric hospitalization. Subjects who score > 5 on the MADRS item 10 (suicide) at screening will be excluded from the study. In addition, a serious suicide or homicide risk, as assessed by evaluating clinician will be considered an exclusion criterion.

Throughout the study, any subject who scores  $\geq 5$  on the MADRS item number 10 will be discontinued from the study. Any subject with scores of  $\geq 6$  on the CGI-I will be discontinued from the study.

Subjects will be informed of any important discoveries made during this study, which may affect their condition or willingness to participate in this study by leaving a message (with subject permission) to contact the study team or by letter, if the subject cannot be reached by phone.

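### The protocol conflicts on whether a stop for clinical deterioration ends only riluzole or also the scheduled assessments, and so on whether later CAPS scores are collected

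*Combined protocol and SAP*

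**What the plan says.** **Stop worded as ending more than the drug.** Section 11.B (Discontinuation of subjects) opens: "Subjects may be discontinued from study treatment and assessments at any time". Among the reasons it lists is clinical deterioration, defined by a 35% rise in CAPS, by "Patients with a CGI-I score ≥ 6 at any post-baseline visit", or by active suicidality as judged by the investigator or "by scoring 5 or more on the item-10 of MADRS". Section 12 (Suicidal Ideation and Imminent Harm) makes two of these obligatory throughout the study. A subject scoring 5 or more "on the MADRS item number 10 will be discontinued from the study", and a subject scoring 6 or more "on the CGI-I will be discontinued from the study".

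**Stop worded as a drug stop.** Section 12 (Protection Against Risks) counts among its safety measures "discontinuation of the study drug and transition to standard clinical treatment should subjects worsen to a sufficient degree". The closing paragraph of 11.B speaks of a subject who "prematurely discontinues (i.e. stops study medication or no longer wishes to participate". The text after the instrument list in Section 11.C has willing subjects who stop medication early keep attending weekly as though still taking it. It names worsening psychological symptoms as one of the things these visits are meant to detect.

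**Section 8 (Privacy).** On clinical deterioration, which it glosses as worsening of PTSD symptoms, a named person "will determine whether: 1) the subject can remain in the study, or; 2) a higher level of care" is needed. No score is mentioned.

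**Analysis.** Specific Aim 1 is the mean change in CAPS over 12 weeks. The Data Analysis section plans intent-to-treat mixed models that use all available data and rely on data being missing at random.

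**The concern.** A coordinator faced with a subject at CGI-I 6 can find support for two different actions: take the subject out of the study, or stop riluzole and keep the visits. The choice decides whether the later CAPS and MADRS ratings of subjects who worsen exist at all. An intent-to-treat analysis needs those outcomes most, because their absence would be tied to how the subject was doing. If they are not collected, the mixed model has to rely on the missing-at-random assumption for them.

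There is also a practical safety side. Section 11.C wants continued evaluations partly to detect worsening after the drug stops, and these are subjects who have already worsened.

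A second, lighter matter is that Section 8 describes a case-by-case decision about remaining in the study without mentioning that Section 12 has already settled it at two scores.

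**Working it through.** The plan gives no figure of its own here. The check is a comparison of the text followed by a count from Table 1.

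**Step 1. The wordings side by side.**

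| Place | What stops | Force |
|---|---|---|
| 11.B, opening | Treatment and assessments | Permissive |
| 12, Suicidal Ideation and Imminent Harm | Participation in the study, at either of two scores | Required |
| 12, Protection Against Risks | Study drug, on sufficient worsening | Descriptive |
| 11.B, closing paragraph | Either medication or willingness to take part | Gloss on early discontinuation |
| 11.C, after the instrument list | Medication; weekly evaluations continue if the subject is willing | General rule |

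The first two rows, read literally, allow or require scheduled assessments to end. The last row says that they continue. No sentence says which prevails for subjects stopped because they worsened.

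**Step 2. Can the phrase about leaving the study be decoded from its use elsewhere?** It cannot. Failure to tolerate 50 mg once daily is a discontinuation from the study under Dosing in Section 11, but a withdrawal from study medication in 11.C. One event carries both wordings, so the phrase alone does not tell staff whether visits end.

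**Step 3. What is lost if visits end.** Inputs from Table 1:
- CGI-I and MADRS are scheduled at all 12 weekly visits, so a required stop can occur at any of them.
- CAPS after baseline is scheduled at visit 6, visit 12 and day 114. Two of these fall in the treatment period and one is post-treatment follow-up.

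Let the stop occur at visit k, after that visit's ratings are done. Weekly MADRS ratings lost = 12 − k.

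| Stop at visit k | Treatment-period CAPS lost | Day-114 CAPS | Weekly MADRS lost (12 − k) |
|---|---|---|---|
| 1 to 5 | 2 of 2 | lost | 12 − 1 = 11 down to 12 − 5 = 7 |
| 6 to 11 | 1 of 2 | lost | 12 − 6 = 6 down to 12 − 11 = 1 |
| 12 | 0 of 2 | lost | 12 − 12 = 0 |

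The day-114 MADRS is lost in every row. If willing subjects continue, no rating is lost by plan.

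**Step 4. Does another assessment fill the gap?** Table 1 has no early-termination CAPS. Section 11.B has the investigator see a subject who stops only where possible, and names no instrument. CAPS after a stop therefore depends on the scheduled visits continuing.

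**Step 5. Section 8.** Section 11.B places both Section 12 scores under clinical deterioration, the term that Section 8 uses. Section 8 has no cross-reference to Section 12 and no exception for the two scores.

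**The case against.** The strongest reply is that the intended reading can be found. Section 11.C states the continue-if-willing rule twice, the closing gloss in 11.B includes stopping medication, and the opening of 11.B permits assessments to end but does not require it. On this view the Section 12 phrase is loose drafting. As an account of likely intent, this stands. It does not remove the conflict: the Section 12 sentence is obligatory, it is specific to subjects who worsen, and nothing subordinates it to 11.C.

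Four stronger readings are tempting, and the documents do not support them.

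- *That clinical follow-up of worsening or suicidal subjects would cease.* Section 12 provides increased contact, more frequent visits or hospitalization for those at risk, and short-term standard treatment for those who stop the drug. Section 11.B follows adverse events as medically necessary. Only scheduled research ratings are in question.
- *That Section 8 authorises keeping a subject whom Section 12 would stop.* Its parenthesis confines it to worsening of PTSD symptoms, whereas MADRS item 10 rates suicidality. Deciding whether a subject remains can also include applying the thresholds. Section 8 is silent on the required stops; it does not contradict them.
- *That the estimated CAPS change is biased.* The documents give no rate for either score, so neither the size nor the direction of any effect can be stated.
- *That the 35% CAPS rise is a discretionary criterion because of the permissive opening of 11.B.* The same opening heads the transaminase stop, which 11.C and Section 12 make mandatory. It settles nothing about the CAPS criterion, and no position is taken here.

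It is also fair to object that a one-hour CAPS interview may be unsuitable for an actively suicidal subject. The fix allows for this.

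**Conclusion.** The conflict over what a deterioration stop ends is real and minor. Under the reading in which visits end, a subject stopped at visits 1 to 5 contributes no treatment-period CAPS after baseline to the primary analysis, and one stopped at visits 6 to 11 contributes one of two. Under the other reading nothing is lost by plan.

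These counts assume that ratings at the stopping visit are completed and that Table 1 is followed. How many subjects would be affected is unknown. The Section 8 point carries little weight: it is a missing cross-reference.

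**What to change.** In 11.B (clinical deterioration) and in Section 12 (Suicidal Ideation and Imminent Harm), word the stop as: 'withdrawn from study medication; willing subjects continue the scheduled visits and CAPS unless the investigator judges this clinically unsuitable'.

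In Section 8, add one clause: the decision described there does not override the stops that Section 12 requires at CGI-I of 6 or more or MADRS item 10 of 5 or more.

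The cost is a few lines of text. No threshold, visit, instrument or form is added, because the visits and CAPS interviews are already in Table 1. The small downside is that some CAPS scores will be taken off drug, possibly on standard treatment. That is compatible with the intent-to-treat analysis already planned, but the report should say so.
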